17. Patients who have prematurely discontinued study drug and have not continued making regular visits (in person or phone) must have Vital Status collected approximately 28 weeks after the patient was randomised.

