### Patients prematurely discontinuing study drug:

Patients who discontinue study drug prematurely should ideally be observed until study end as if they were still receiving blinded study treatment. There are 4 Options for observing patients after premature drug discontinuation. See [Section 3.3.4.1](#)

**Early D/C Option 1:** For patients who prematurely discontinue taking study drug who are willing to conduct the remaining visits, the following should be performed:

- EOT Visit must be performed within 7 days of last intake of study drug, or as soon as possible.
- Thereafter, patients should be followed up according to the regular visit schedule through Visit 16.
- A Follow-Up Visit is not necessary if the patient discontinued >4 weeks prior to Visit 16. If a patient discontinues <4 weeks prior to Visit 16, a Follow-up Visit will be performed 28 days after the EOT Visit.

**Early D/C Option 2:** For patients who prematurely discontinue taking study drug who are willing to conduct the remaining visits over the phone, the following should be performed:

- EOT Visit must be performed within 7 days of last intake of study drug, or as soon as possible.
- A Follow-up Visit will be performed 28 days after the EOT Visit.
- Thereafter, patients should be followed up over the phone according to the regular visit schedule through Visit 16. See [Section 3.3.4.1](#) for Early D/C Option 2 which details the assessments to be conducted via phone.

**Early D/C Options 3 and 4:** For patients who prematurely discontinue study drug and agree to be contacted or have information collected from an alternative source at the end of the study, the following should be performed:

- EOT Visit must be performed within 7 days of last intake of study drug, or as soon as possible.
- A Follow-up visit will be performed 28 days after the EOT Visit.
- Occurrence of psychiatric illness/relapse and vital status must be collected approximately 28 weeks after the patient was randomised.

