### 7.3.1 Primary endpoint analyses

The primary endpoint is the time to first relapse as defined in [Section 2.1.2](#) over the ITT follow-up period (see definition in [Section 7.3](#)).

The treatment comparison strategy is specified in [Section 7.2](#). The treatment arms will be pooled according to dose, i.e. no distinction will be made between treatment arm randomised to taper or treatment arm randomised to withdrawal.

The equality of the hazard rates will be tested by the Wald test for the treatment effect in a stratified Cox proportional hazards model at the two-sided 5% significance level. The model includes the treatment effect as the only covariate and is stratified by country. Breslow's method for handling ties will be used.

The same stratified Cox proportional hazards model will be used to estimate the hazard ratio of BI 409306 vs. placebo and the asymptotic 95% Wald confidence interval. A hazard ratio of less than one favors BI 409306. The analysis will be implemented using SAS® PROC PHREG. Cox proportional hazard model assumptions will be verified.

In early discontinued patients, if the occurrence of a relapse cannot be determined between the time of discontinuation and last contact, it is assumed that no relapse has occurred. Patients who discontinue study medication will be followed until the end of the trial for the primary endpoint. Patients who are lost-to-follow up will be censored for the primary endpoint at the date of last known patient contact.

A sensitivity analysis will be conducted on the primary endpoint, using the Full Follow-up period (see definition above).

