### 7.7 DETERMINATION OF SAMPLE SIZE

Sample size considerations are given in Table 7.7: 1 based on background placebo relapse rates of 25% and 30% and for hazard reductions for the combined BI 409306 groups vs.

placebo ranging from 45% to 55%, 80% power, a two-sided alpha = 0.05, and 20% dropout after six months.

Table 7.7: 1 Trial sample sizes for selected assumptions of hazard ratios and proportions of placebo failures, with 20% dropout, 80% power, and  $\alpha=0.05$

Placebo failure rate	Hazard reduction a for BI 409306 (both groups combined) to placebo		
	55% a	50% a	45% a
30%	305	385	494
25%	372	470	603

a 55% hazard reduction is the same as a hazard ratio of 0.45; 45% hazard reduction is the same as a hazard ratio of 0.55

The sample size selected was 385 under the assumption that the relapse rate for placebo is 30% and the hazard reduction for BI 409306 is 50%. One hundred twenty-nine (129) patients will be randomised per treatment group in a 1:1:1, making the target total number of randomised patients to be 387.

Seventy-four (74) events (relapses) are needed to be observed to meet the trial objective of 80% power for the comparison of BI 409306 (N=258 for 25 mg q.d. and 50 mg q.d. combined) to placebo (N=129). This will not be an event driven trial, so the trial will end when all randomised patients have reached 6 months exposure, regardless of number of conversions observed.

Calculations were performed using ADDPLAN® 6.1.1 statistical package by [REDACTED].

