7.4.1 Primary efficacy analysis

The primary analysis will be conducted on the FAS using the ITT follow-up period as defined in Section 6.1. Because the ITT covers the 28 weeks of planned treatment and not the T/W period, the treatment arms will be pooled according to dose and disregarding the T/W randomization.

Revised CTP in Section 7.3.1:

The equality of the hazard rates will be tested by the Wald test for the treatment effect in a stratified Cox proportional hazards model at the two-sided 5% significance level. The model includes the treatment effect as the only covariate and is stratified by country. Breslow's method for handling ties will be used.

The same stratified Cox proportional hazards model will be used to estimate the hazard ratio of BI 409306 vs. placebo and the asymptotic 95% Wald confidence interval. A hazard ratio of less than one favors BI 409306. The analysis will be implemented using SAS® PROC PHREG. Cox proportional hazard model assumptions will be verified.

In early discontinued patients, if the occurance of a relapse cannot be determined between the time of discontinuation and last contact, it is assumed that no relapse has occurred. Patients who discontinue study medication will be followed until the end of the trial for the primary endpoint. Patients who are lost-to-follow up will be censored for the primary endpoint at the date of last known patient contact.

According to the CTP, we have specified more details regarding efficacy analysis using ITT FU and Full FU:

Definition of last at-risk date:

The last at-risk date determined as the latest date among: the date of first dose of study medication, the date of last drug administration, all the visit start dates (including phone contact dates in which the patient was reached and follow-up contact dates) and start or stop dates of events reported on the adverse event forms.

If a patient dies, the date of death is their last at-risk date.

Definition of Visit 16 date:

The date of Visit 16 for the determination of the ITT FU period end date will be the start date recorded on eCRF.

Time to event calculations:

A. Patients completing treatment period and study period (for ITT analysis):

Events (relapses) are counted in the ITT time to event analysis whenever they occur between the first dose of randomized treatment and the patient's Visit 16 date or the date of last dose if this occurred after visit 16. (In SDTM this is EPOCH=TREATMENT1)

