- Patients who chose Early Discontinuation Option 5, i.e. withdrew consent per CTP (for ITT and Full FU analysis): Events (relapses) are counted in the time to event analysis whenever they occur between the first dose of randomized treatment and the patient's date of consent withdrawal.
 - Patients with event counted: <date of event> <date of first drug administration> +1
 - Patients without event counted: <date of consent withdrawal> <date of first drug administration >+1 day
- Patients who are Lost-to-Follow-up (for ITT analysis): Events (relapses) are counted in the time to event analysis whenever they occur between the first dose of randomized treatment and the last at-risk date.

- Patients with event counted: <date of event> <date of first drug administration> +1 day
- Patients without event counted: <date of last at-risk> <date of first drug administration >+1 day

*Please note: Patients who are LTFU during the study (regardless of initial Early Discontinuation choice), but were successfully found towards the end of study via a vital status call, will be included in the Full-FU analysis period by replacing as follows:

• Patients without event counted: <date of vital status/date of EOS> – <date of first drug administration >+1 day

The following SAS code will be used:

```
proc phreg data= primary;
   CLASS &trt.(ref="Placebo") / order=internal;
   model aval*cnsr(1) = &trt./ties=breslow;
   strata countrdc;
   hazardratio 'HR' &trt. /diff=ref cl=both;
run;
```

Subgroup analyses will be performed on the subgroups specified in Section 6.4. Definition of Japanese patients is provided in Section 9.1. The same model as described above for the primary efficacy analysis, will be used for these analyses.

The following SAS code will be used for survival plot:

```
proc lifetest data=primary method=km plots=survival(failure test
atrisk);
time aval*cnsr(1);
id usubjid;
strata &trt. /test=logrank;
run;
```

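### Discontinuers whose relapse status stays undetermined are analysed as relapse-free up to last contact or end of study, which biases the primary hazard ratio towards whichever arm has more of them

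*Protocol*

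**What the plan says.** - **The rule.** Protocol 7.3.1 covers early discontinuers in whom relapse "cannot be determined between the time of discontinuation and last contact, it is assumed that no relapse has occurred". SAP 7.4.1 keeps it unchanged ("it is assumed that no relapse has occurred").
- **How it is applied.** SAP 7.4.1 part D takes Option 3 and 4 patients who complete the required study period without a counted event to the end-of-study (EOS) date, in both the ITT and Full follow-up analyses. Ascertainment of relapse is not a condition. The last at-risk date used elsewhere in that section is built from dosing, visit, contact and adverse-event dates, not from dates on which relapse was assessed.
- **What is collected at week 28.** Protocol 6.2.2 says for Options 3 and 4: "Occurrence of psychiatric illness/relapse and vital status must be collected approximately 28 weeks after the patient was randomised". Flow Chart footnote 17 is narrower. It says that patients who stopped drug and no longer make regular visits "must have Vital Status collected approximately 28 weeks after the patient was randomised", and does not mention relapse.
- **Lost patients.** In the ITT analysis they are censored at last contact (Protocol 7.3.1) or the last at-risk date (SAP 7.4.1). In the Full follow-up analysis, lost patients who "were successfully found towards the end of study via a vital status call, will be included in the Full-FU analysis period" have their time extended to that date. SAP 6.6, however, censors any patient without relapse at the planned end of the 28 weeks.
- **Sensitivity analyses.** SAP 7.4.2 plans the Full follow-up analysis and a composite of treatment discontinuation or relapse.

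**The concern.** Knowing that a patient was alive at week 28 does not show that the patient had not relapsed. When status is undetermined, the rule removes any unseen relapse from the event count and leaves the patient in the risk set. Both lower the apparent relapse rate of that arm. If undetermined patients are spread unevenly between arms, the primary hazard ratio moves towards the arm with more of them. The Full follow-up analysis cannot reveal this, because it applies the same assumption to more patients.

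**Working it through.** **1. The plan's own figures.** Protocol 7.7 uses "80% power, a two-sided alpha = 0.05, and 20% dropout after six months", assumes that "the relapse rate for placebo is 30% and the hazard reduction for BI 409306 is 50" per cent, and allocates 258 pooled active to 129 placebo patients (2:1).

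- Events = (1.960 + 0.842)² / [(1/3)(2/3)(ln 0.5)²] = 73.5, so 74, as stated.
- In units of 28 weeks, the placebo hazard is −ln 0.70 = 0.357, the active hazard 0.178 and the dropout hazard −ln 0.80 = 0.223. The chance of an observed relapse is (0.357/0.580)(1 − 0.56) = 0.271 on placebo and (0.178/0.401)(1 − 0.669) = 0.147 on active.
- The 2:1 average is 0.188, and 73.5/0.188 is about 391, within 2% of the stated 385. Dividing by 0.8 instead gives 440, which does not match. The sample size thus behaves as if dropouts stop contributing time, unlike the rule.

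**2. Effect of the rule.** Assumptions: 30% placebo relapse; exponential hazards, unchanged after stopping; a share u of an arm stops at a time uniform over the 28 weeks and stays undetermined. The documents give no value of u, so a range is shown.

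With true hazard ratio 1 and nothing seen after stopping:

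- Relapse probability seen in an undetermined patient: 1 − 0.30/0.357 = 0.159, against 0.30 in a fully followed patient.
- Time at risk credited: 0.159/0.357 + 0.159/0.357 = 0.891 (before stopping, then carried forward), against 0.30/0.357 = 0.841.
- Apparent rate in the arm = (0.30 − 0.141u)/(0.841 + 0.050u).
- 20% active against 10% placebo: (0.2718/0.8511)/(0.2859/0.8461) = 0.319/0.338 = 0.945.

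If relapse is still seen up to the Follow-up Visit 28 days after end of treatment (EOT), the rate becomes (0.30 − 0.102u)/(0.841 + 0.031u). The large-sample Cox estimates, from the score equation with 2:1 allocation, agree with these rate ratios to within about 0.002:

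| Undetermined, active vs placebo | True HR 1, nothing seen after stopping | True HR 1, relapse seen to EOT + 28 days |
|---|---|---|
| 5% vs 2.5% | 0.987 | 0.991 |
| 10% vs 5% | 0.973 | 0.981 |
| 20% vs 10% | 0.945 | 0.962 |
| 30% vs 10% | 0.892 | 0.924 |
| 10% vs 20% | 1.058 | 1.040 |
| 20% vs 20% | 1.000 | 1.000 |

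With a true hazard ratio of 0.50 and nothing seen after stopping, 20% vs 10% gives 0.475 and 30% vs 10% gives 0.449. With equal 20% shares the null ratio is unchanged, but apparent placebo relapse falls to 0.30 − 0.141 × 0.2 = 27.2%.

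**3. False-positive rate in the drug's favour (nominal 0.025).** Use Φ(−ln HR × √(2D/9) − 1.96), with D the events expected from 387 patients.

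- 20% vs 10%, nothing seen: HR 0.945, D = 107, giving Φ(0.27 − 1.96) = 0.046.
- 30% vs 10%, nothing seen: HR 0.892, D = 103, giving 0.079.
- 10% vs 5%, relapse seen to EOT + 28 days: HR 0.981, D = 113, giving 0.031.

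SAP 4 reports that recruitment stopped early. Fewer events would make this inflation smaller but would leave the bias in the hazard ratio as it is.

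**4. Censoring instead.** Censoring at the last ascertained date returns 1.00 or 0.50 in every case above, because the hazard was assumed not to change after stopping. If it doubles after stopping (30% vs 10%, true HR 1 on a common hazard otherwise, nothing seen afterwards), complete follow-up would give 1.08, the plan's rule 0.89 and censoring 1.00. Censoring is then less biased, but not unbiased.

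**The case against.** The defence of the plan is substantial, and most of it stands.

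- **Most discontinuers stay observed.** Protocol 3.3.4.1 asks patients to take the most rigorous follow-up they will accept. Options 1 and 2 keep PANSS, CGI-S and C-SSRS.
- **Follow-up does not end at EOT.** Options 2 to 4 have a Follow-up Visit 28 days later (Flow Chart footnote 5, Protocol 6.2.2 and 6.2.3). As the Flow Chart reads, it includes C-SSRS, adverse events and concomitant therapy, which bear on several relapse criteria. A reader might infer that a patient who stops at week 6 adds 22 wholly unobserved weeks. That visit does not support this.
- **The relapse question already exists.** Protocol 3.3.4.1 and 6.2.2 require it at week 28. Footnote 17 looks like an abbreviation, so the rule bites only when the required collection fails.
- **Lost patients and consent withdrawals are not carried forward in the ITT analysis** under SAP 7.4.1.
- **The composite in SAP 7.4.2** counts discontinuation as an event, so it credits no time after stopping and would expose an imbalance. It answers a different question, however, and does not correct the primary hazard ratio.
- **The large scenarios are near worst cases.** Undetermined shares of 20 to 30% equal or exceed the whole planned dropout of 20%. Protocol 4.1.2 describes adverse events at both doses as similar to placebo, so no imbalance is foreseen.

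None of this removes the rule or makes ascertainment a condition of reaching the EOS date.

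**Conclusion.** The concern holds in a limited form. As written, the plan turns undetermined status into relapse-free time in the primary analysis. What drives the bias is the difference between arms in undetermined patients. A reader might infer that any difference in discontinuation is enough, or that the rule favours the drug. Neither follows: discontinuers under Options 1 and 2 remain assessed, and the direction reverses if placebo has more undetermined patients.

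The likely size is small. The null hazard ratio is about 0.98 to 0.99 at 5 to 10% active against 2.5 to 5% placebo undetermined, with relapse seen to EOT + 28 days. It reaches about 0.945 to 0.96 at 20% vs 10% and about 0.89 to 0.92 at 30% vs 10%, and is 1.00 with equal shares. All of this rests on 30% placebo relapse, exponential hazards, uniform discontinuation and assumed shares. It should be corrected because the correction is cheap and neither planned sensitivity analysis isolates the assumption.

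**What to change.** 1. In Protocol 7.3.1 and SAP 7.4.1, including part D, censor a patient with undetermined status at the last date on which relapse status was ascertained. Use the EOS or vital-status date only if that contact or record review recorded relapse as yes or no, and count any relapse recorded. Apply the same condition to the lost-to-follow-up note for the Full follow-up analysis.
2. Keep the present rule as a sensitivity analysis. Add a delta-adjusted or tipping-point analysis, because censoring is itself informative if the hazard rises after stopping.
3. Align Flow Chart footnote 17 with Protocol 6.2.2, so that relapse is named alongside vital status.
4. Reconcile SAP 6.6 (censoring at planned week 28) with the last-contact rule for lost patients in Protocol 7.3.1 and SAP 7.4.1. Read literally, SAP 6.6 extends the same problem to lost patients.
5. Report the number of undetermined patients by arm, so that the reader can place the trial in the range above.

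Cost: wording, one derivation flag, one added sensitivity analysis and slightly less person-time in the primary analysis. No new data collection is needed, since Protocol 6.2.2 already requires the relapse question.

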### 7.3.2 Secondary endpoint analyses

#### Key secondary analysis

The key secondary analysis is a restricted maximum likelihood (REML) based approach using a mixed model with repeated measurements (MMRM) comparing the change from baseline of PANSS positive symptoms score after 28 weeks of treatment (Section 7.2). The analysis will include the fixed, categorical effects of treatment at each visit, and the fixed continuous effects of baseline at each visit. Visit will be treated as the repeated measure with an unstructured covariance structure used to model the within-patient measurements. The statistical model will be as follows:

$$y_{ijkm} = \beta_j S_i + \tau_{jk} + \phi_m + e_{ij}$$
$$e_{ij} \sim N_Z(\mathbf{0}, \Sigma).$$

$y_{ijkm}$  = response variable for subject  $i$  in country  $m$  at visit  $j$  receiving treatment  $k$

$S_i$  = the baseline measurement of subject  $i$ ,  $i=1,2,\dots$

$\beta_j$  = coefficient of baseline effect at visit  $j$

$\tau_{jk}$  = the effect of treatment  $k$  at visit  $j$ ,  $j=1,\dots,Z$  and  $k=1,\dots,Y$

$\phi_m$  = the effect of country  $m$ ,  $m=1,\dots,X$

$e_{ij}$  = the random error associated with the  $j^{\text{th}}$  visit of the  $i^{\text{th}}$  subject. Errors are independent between subjects.

$\Sigma$  = an unstructured covariance matrix.

The Kenward-Roger approximation will be used to estimate denominator degrees of freedom and adjust standard errors. Significance tests will be based on least-squares means using a two-sided  $\alpha = 0.05$  or the remaining alpha (two-sided  $((1 - \alpha) \%)$  confidence intervals). The treatment comparison will be the contrast between treatments at the endpoint visit.

The key secondary analysis will be performed on the FAS. Patients will be analysed according to the stratum to which they belong (regardless of any mis-assignment to treatment based on identification of the wrong stratum), as such an error occurs before randomisation and is therefore consistent with regulatory guidance.

Procedures to follow if the analysis fails to converge will be described in the TSAP.

To assess the homogeneity of the treatment effect on the primary endpoint across the levels of the country stratification, the same MMRM model will be fitted but replacing the treatment-by-visit term by a treatment-by-country-by-visit term. A descriptive p-value of treatment effect homogeneity at 28 weeks will be calculated. No overall treatment effect will be estimated from this model as it is not interpretable.

### Secondary analysis

Time to change in antipsychotic medication will be analysed in the same manner as the primary endpoint using the stratified Cox proportional hazards model.

Additionally, the analyses for suicidal ideation and behaviour as assessed by C-SSRS will be analysed by calculating a relative risk reduction and providing a 95% confidence interval around the RRR.

The PGI-I score, change in CGI-S and PSP will be summarized descriptively.

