Statistical methods:	For the primary endpoint of time to relapse, the equality of the hazard rates will be tested by the Wald test for the treatment effect in a stratified Cox proportional hazards model. The model includes treatment as the only covariate and is stratified by country.

	Secondary endpoints will be analysed descriptively using relative risk ratios and 95% confidence intervals.
--	---

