Study 1289.18 was conducted to assess safety, tolerability, PK and pharmacodynamics (PD) of BI 409306 25 mg, 50 mg, or 100 mg once a day (q.d.) for 14 days in patients with mild-to-moderate schizophrenia. Satisfactory safety and tolerability were observed while PK mirrored that of healthy volunteers. Recently completed study 1289.6 (proof of concept study in patients with cognitive impairment associated with schizophrenia (CIAS)) failed to achieve the primary endpoint of improving cognition as assessed by the MATRICS Consensus Cognitive Battery (MCCB), however demonstrated acceptable safety and tolerability at all doses. The percentage of subjects with any AE increased with increasing BI 409306 dose, ranging from 33.3% in the 10 mg group to 53.5% in the 100 mg group. The incidence of AEs in the 10 mg and 25 mg dose groups was similar to that of the placebo group. Most AEs were mild or moderate in intensity, with only 2 subjects in the BI 409306 groups and 4 subjects in the placebo group experiencing severe adverse events (AEs). Most striking was the finding that Serious AEs (SAEs), including 8/8 psychiatric SAEs, were only reported in the placebo group vs. none in the active arms. Further, it was noted that results of the C-SSRS showed suicidal ideation was reported in no subjects in the 10 mg group, 1 subject (1.2%) in the 25 mg group, 2 subjects (2.5%) in the 50 mg, 1 subject (1.2%) in the 100 mg group, and 6 subjects (3.6%) in the placebo group. It was further noted that the severity of the suicidal ideation present was more severe within the placebo subjects, with 3 placebo subjects reporting "Active suicidal ideation with any methods (not plan) without intent to act" and one subject reporting "Active suicidal ideation with some intent to act, without specific plan" vs. zero such findings in the active dose groups [[c01694347-09](#); [c09340078-01](#)].

None of the safety data presented a safety issue for further clinical trials.

For a more detailed description of the BI 409306 profile, including pharmacokinetics and pharmacodynamics, please refer to the current Investigator's Brochure (IB) [[c01694347-09](#)].

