### 7.5 HANDLING OF MISSING DATA

All patients will be followed up for relapse to the greatest possible extent as described in [Section 3.3.4.1](#). Any patient who has not relapsed will be censored in the analysis of the primary endpoint at the time of last patient contact. For any secondary analysis using RRR, all patients in the FAS will be included in the calculation of the RRR, regardless of dropout.

For the key secondary analyses, if a patient misses a visit, the data will not be imputed. The mixed effects model will handle missing data based on a likelihood method under the “missing at random” assumption.

Further details about handling missing data will be specified in the TSAP.

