### 7.6 RANDOMISATION

Patients will be randomised in blocks to double-blind treatment equally to three treatment arms (25 mg q.d. BI 409306, 50 mg q.d. BI 409306 or placebo). Additionally, patients will be randomised equally to a one-week taper or withdrawal period immediately after the 28 week treatment discontinuation. The randomisations will occur together using the IRT in a 1:1:1:1:1:1 ratio. The randomisation will be stratified by country.

BI will arrange for the randomisation and the packaging and labelling of trial medication. The randomisation list will be generated using a validated system, which involves a pseudo-random number generator so that the resulting treatment will be both reproducible and non-predictable. The block size will be documented in the Clinical Trial Report. Access to the codes will be controlled and documented.

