7.5.2 (Other) Secondary endpoint(s)

Secondary endpoints will be analyzed as described in section 7.3.2 in the revised CTP:

Time to change in antipsychotic medication will be analysed in the same manner as the primary endpoint using the stratified Cox proportional hazards model.

Additionally, the analyses for suicidal ideation and behaviour as assessed by C-SSRS will be analysed by calculating a relative risk reduction and providing a 95% confidence interval around the RRR.

The following SAS code will be used for RRR:

```
proc freq data=patdata;
  tables trtp*avalc /chisq RELRISK;
  ods output
RelativeRisks=rr(where=(lowcase(STUDYTYPE)='Cohort (Coll Risk)')
rename=(value=compestimate lowercl=complower uppercl=compupper))
ChiSq=chi(where=(lowcase(STATISTIC)='chi-square') rename=prob=comppvalue);
run;
```

The PGI-I score, change in CGI-S and PSP will be summarized descriptively.

For the secondary endpoints summary, the worse case scenario data will be analyzed if multiple assessments are completed during the same visit window.

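### The C-SSRS relative risk reduction is coded as a crude ratio with large-sample limits: it ignores the country strata and has no confidence interval if a compared arm has no events, which is possible rather than likely at 129 per arm.

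*Protocol*

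**What the plan says.** The protocol synopsis makes the analysis descriptive: "Secondary endpoints will be analysed descriptively using relative risk ratios and 95% confidence intervals". Protocol 7.3.2 then says that suicidal ideation and behaviour on the C-SSRS "will be analysed by calculating a relative risk reduction and providing a 95% confidence interval around the RRR" (RRR, relative risk reduction), and names no interval method. Protocol 7.5 fixes the denominator: "For any secondary analysis using RRR, all patients in the FAS will be included in the calculation of the RRR, regardless of dropout".

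The method is settled only in SAP 7.5.2, where the PROC FREQ code requests "tables trtp*avalc /chisq RELRISK". The table has no country variable, and the code asks for no Mantel-Haenszel, score or exact limits. Neither document has a rule for an arm without events. Neither says whether the RRR is for the pooled doses, each dose or both, or how the C-SSRS is reduced to a binary outcome.

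By contrast, protocol 7.6 states "The randomisation will be stratified by country", the primary Cox model is stratified by country, and the mixed model for the key secondary endpoint carries a country effect.

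**The concern.** Limits computed on the log risk ratio need at least one event in each compared arm. Suicidality outcomes are sparse. In the previous trial of this drug in schizophrenia (1289.6, protocol 1.2), "suicidal ideation was reported in no subjects in the 10 mg group"; the same paragraph reports "1 subject (1.2%) in the 25 mg group, 2 subjects (2.5%) in the 50 mg" group, and "6 subjects (3.6%) in the placebo group". The 10 mg dose is not a treatment arm here, but its empty cell shows that the case can arise.

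If a BI 409306 arm has no events, the estimated RRR is 100% and the planned interval does not exist. If placebo has none, the ratio itself is undefined. The interval would then be missing for a safety-relevant outcome just where the point estimate is most extreme. The SAP gives the mixed model a six-step fallback for non-convergence but provides none here.

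Leaving out country is a smaller matter: the analysis does not follow the randomisation, while the two main efficacy models do.

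**Working it through.** **Arm size.** The documents give no sample-size figure for the C-SSRS endpoint. The 129 per arm comes from the primary endpoint (protocol 7.7). With a hazard ratio of 0.50, 2:1 allocation, two-sided alpha 0.05 and 80% power, events = (1.960 + 0.842)² / [(2/9)(ln 0.5)²] = 73.5, which rounds up to the stated 74. Exponential relapse (30% on placebo) with exponential 20% dropout gives N of about 391, against 385 stated. So 129 per arm is taken as planned.

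**Rates.** 25 mg 1.2%, 50 mg 2.5%, placebo 3.6% (protocol 1.2). They come from a 12-week trial (protocol 9.2), and this trial treats for 28 weeks. Scaling under a constant hazard is an assumption: p28 = 1 − (1 − p)^(28/12), giving 2.8%, 5.7% and 8.2%. Expected events per 129 patients are 1.5, 3.2 and 4.6 unscaled, and 3.6, 7.4 and 10.6 scaled.

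**Why the limits fail.** The standard error of log RR is √(1/x1 − 1/n1 + 1/x0 − 1/n0), with x events among n patients in each arm. It is undefined when x1 or x0 is zero.

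**Chance of no interval.** Let a = (1 − p1)^n and b = (1 − p0)^n. The chance that at least one of the two arms is empty is a + b − ab. For 25 mg against placebo at n = 129 and the 12-week rates, a = 0.988^129 = 0.211 and b = 0.964^129 = 0.009, so the chance is 0.218. For the pooled doses, a = (0.988 × 0.975)^129 = 0.008.

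| Contrast with placebo | 129 per arm, 12-week rates | 129 per arm, scaled | 65 per arm (assumed), 12-week rates | 65 per arm, scaled |
|---|---|---|---|---|
| 25 mg | 22% | 2.6% | 51% | 16% |
| 50 mg | 4.7% | 0.05% | 27% | 2.5% |
| Pooled | 1.7% | below 0.01% | 17% | 0.7% |

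The 65 per arm is illustrative. SAP section 4 says recruitment stopped early and the analyses were left unchanged, but gives no achieved size.

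**Narrower outcome.** One placebo patient in the previous trial had ideation with some intent. The placebo group was about 6/0.036 = 167 patients. At 1/167, placebo itself has no such event among 129 patients with probability (1 − 1/167)^129 = 46%, or 16% when scaled.

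**What a score interval gives on the same data.**
- 0/129 against 5/129: no log-scale interval exists. Score limits give RR 0 (95% CI 0 to 0.76), so RRR = 1 − RR is 100% (24% to 100%). The Miettinen-Nurminen risk difference is −3.9% (−8.8% to −0.9%).
- 2/129 against 5/129: RR 0.40, log-scale limits 0.08 to 2.02, score limits 0.09 to 1.75. With events in both arms the two methods differ only modestly.

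**The case against.** The strongest objection is to a reading that the previous rates make an empty dose arm likely. A reader might infer this from the 1.2% at 25 mg. The documents do not support it. At 129 per arm the chance is about one in five on unscaled 12-week rates and under 3% once scaled to this trial's duration. The larger figures need an arm size or an outcome definition that the documents do not give.

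A reader might also infer that a 100% reduction would be reported with no sign of its uncertainty. That goes too far. SAP section 7 requires counts and percentages by treatment group, and the 7.5.2 code outputs a chi-square p-value. Suicidal behaviour and type 4 or 5 ideation are also components of the primary endpoint, which has a country-stratified analysis, and they must be reported as serious adverse events. What would be lost is the interval itself.

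On country, the endpoint is descriptive and no alpha is at stake. The other descriptive scales are not adjusted either. A handful of events would be spread over four countries (protocol 3.3) or six (SAP 5.4.1). No numerical gain from stratifying has been shown, so this part rests on consistency with the design.

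It is also fair to say that the protocol sentence alone does not reveal the method; the evidence is the SAP code. In addition, SAP section 4 assigns hazard ratios to the primary and secondary endpoints and the RRR to further endpoints, which sits awkwardly with 7.5.2 and should be reconciled.

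What stands after all this: the code is unstratified, its limits fail with an empty arm, and no fallback is written.

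**Conclusion.** The point holds as a modest improvement to a descriptive analysis, not as a threat to any confirmatory claim. The planned interval fails in about 22% of trials for 25 mg against placebo at the 12-week rates and about 3% if scaled; for 50 mg, about 5% and 0.05%; for the pooled doses, 2% or less. These figures assume 129 patients per arm in the full analysis set, event rates equal to those reported for ideation in the previous trial, and, for the scaled values, a constant hazard. With an assumed 65 per arm, the 25 mg figure is 51% unscaled and 16% scaled. The ranges are wide because the achieved size, the binary outcome and the contrasts are not stated.

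**What to change.** In SAP 7.5.2:
- Keep the RRR, and replace the default limits with score limits of the Miettinen-Nurminen type.
- Stratify by country with Mantel-Haenszel weights where counts allow, and say what is done when they do not.
- When placebo has no events, report the risk difference with its score interval in place of the RRR.
- Name the contrasts and the binary C-SSRS outcome, so that the rule can be applied without a choice after unblinding.

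The cost is a few lines of text and code on data already collected, plus a supplementary risk difference in the output. It does not touch patients, visits or the testing hierarchy. Stratifying should change the numbers little at these event counts. Making the risk difference the headline measure is unnecessary, because score limits preserve the RRR that the protocol planned.
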